14. PROVISIONS TO MONITOR THE DATA TO ENSURE THE SAFETY OF SUBJECTS*

The study presents minimal risk to participants for participating in the study. However, there is a possibility of the breach of confidentiality. Participants can opt out of the survey at any time during the study. Additionally, participants' identities will never be revealed. Names, addresses, email addresses, or any other identifying information will not be collected. Participants are identified by a unique, randomly generated code at the end of the survey only to ensure they have completed it and are compensated.

15. WITHDRAWAL OF SUBJECTS WITHOUT THEIR CONSENT*

NA

16. RISKS TO SUBJECTS*

Risks to subjects involve being uncomfortable answering questions about tobacco use or seeing messages about negative health effects of using e-cigarettes.

17. POTENTIAL DIRECT BENEFITS TO SUBJECTS*

NA

18. VULNERABLE POPULATIONS*

- **Students or employees:** Students or employees of the University of Massachusetts Medical School will be eligible to enroll. Contacts with the study participants will be for assessment purposes only.
- **Adults unable to consent:** They are ineligible to participate.
- **Subjects who are not yet adults (infants, children, teenagers):** Individuals under the age of 18 are ineligible to participate.
- **Pregnant women:** Pregnant women may be included in this research study. These requirements will be followed: No inducements, monetary or otherwise, will be offered to terminate a pregnancy. Individuals engaged in the research will have no part in any decisions as to the timing, method, or procedures used to terminate a pregnancy. Individuals engaged in the research will have no part in determining the viability of a neonate.
- **Neonates of uncertain viability or non-viable neonates:** NA
- **Prisoners:** We will not enroll or conduct research procedures with individuals that are known to be prisoners. We will not obtain any information regarding participants' incarceration status.

19. MULTI-SITE RESEARCH*

INVESTIGATOR STUDY PLAN - REQUIRED

NA

20. COMMUNITY-BASED PARTICIPATORY RESEARCH*

NA

21. SHARING OF RESEARCH RESULTS WITH SUBJECTS*

Results of this research may be shared with other researchers upon request. We will not collect information linked to the identity of individual subjects. Additionally, dataset will be de-identified to remove any identifying information, such as IP addresses, prior to sharing with other researchers.

22. SETTING

The study will take place online via Prolific, an online crowdsourcing platform. Participants may participate in the survey in any setting (e.g., home, library, computer lab) with computer or mobile devices with Internet access. The research team will conduct data entry and analysis from Albert Sherman building. It is possible that the research team conducts data entry and analysis outside the campus (e.g., research team members' home). In such cases, they will be using the UMass Medical computer with the UMass Medical Secure network.”

23. RESOURCES AVAILABLE

The **PI** and **postdoctoral fellow** are responsible and accountable for the implementation of the study in accordance with the proposed plan. The postdoctoral fellow is responsible for obtaining the informed consent. The PI and the postdoctoral fellow hold a doctoral degree and has extensive human subjects research experience including the conduct of a variety of studies relevant to the current study. The postdoctoral fellow will devote 50% of their time to ensure the launch and completion of this study, as well as data cleaning, analysis, and dissemination. The PI and/or postdoctoral fellow will meet with any staff member involved with this research via Zoom and in person to ensure that they are fully informed about the protocol and the research procedures. Furthermore, the PI and/or postdoctoral fellow will meet with the staff members at least once a week to review their specific duties and functions (e.g., setting up study, data analysis).

24. LOCAL RECRUITMENT METHODS

We will recruit U.S. young adults (N=800; 18-24 years) identified as vapers (n=400) and susceptible non-vapers (n=400) to collect self-report measures. Vapers are defined as those who have vaped in the past 30 days,^{2,55} and susceptible non-vapers are defined as those who have never vaped, or those who have ever vaped but not in the past 30 days, but are susceptible to use as determined by the Susceptibility to Use Tobacco Products questionnaire.⁵⁶ We will use Prolific, a crowdsourcing platform.⁵⁷ Prolific is optimal for this type of behavioral experiment⁵⁸ because it allows a rapid collection of high quality data.⁵⁷ Our team has successfully recruited participants and completed studies using Prolific.^{59,60} Using an online convenience sample has yielded comparable results with probability samples in prior tobacco survey research studies.^{61,62} We will use Prolific's screening features to recruit participants based on their vaping status (vapers and susceptible non-vapers), age (18-24 years), English fluency, and location (U.S.). We will use all data assurance measures (e.g., attention checks, manual review, bot inspection) for data quality, as we have done in past crowdsourced studies.^{59,63} Participants sign up to be on the

INVESTIGATOR STUDY PLAN - REQUIRED

Prolific platform as participants and can self-select what studies they want to participate in. However, the study will not use advertisements to directly recruit participants for this study. Participants who complete the study will receive \$4.00 via Prolific per its policies for participating in a 20-minute survey. This study will not be advertised specifically to recruit UMass Chan students. It is possible that UMass Chan students who signed up to be on the Prolific platform might participate in the study.

25. LOCAL NUMBER OF SUBJECTS

800 individuals who are age between 18 and 24 years old, speak English, current residents of the United States will participate in the study.

26. CONFIDENTIALITY

Questionnaire data will be collected using the Qualtrics data collection system via Prolific. IP addresses will not be collected. No identifiable data will be collected via the Qualtrics research system. Data will be collected anonymously with no direct or indirect link or awareness of who participated in the study. All data will be stored on a secure UMass Chan server. Data will be password protected and stored for seven years, then destroyed as is the standard in the health communication field.

[name] and the research coordinator (postdoctoral fellow) will be responsible for file maintenance. Participant consent form and survey and data will be stored on a password protected storage on a UMass Chan Medical secured network. Files will be reviewed once per week to ensure all documentation is securely stored.

27. PROVISIONS TO PROTECT THE PRIVACY INTERESTS OF SUBJECTS

All study activities will be conducted in a private setting. Subjects will be told that they can skip any question they wish.

28. COMPENSATION FOR RESEARCH-RELATED INJURY

This research presents minimal risk. No funds have been set aside for compensation.

29. ECONOMIC BURDEN TO SUBJECTS

None.

30. CONSENT PROCESS

Informed consent will be obtained using a Fact Sheet. All members of the research team will be trained in Human Subjects and HIPAA policies and procedures and the handling of data to ensure confidentiality in order to obtain Institutional Review Board (IRB) approval from UMass Chan. Researchers' contact information (phone and email) will be provided with study description for participants to ask questions.

31. PROCESS TO DOCUMENT CONSENT IN WRITING

We will use a Fact Sheet to indicate that we will not document consent in writing since the research is minimal risk and involves no procedures that require a signature outside of the research context.

INVESTIGATOR STUDY PLAN - REQUIRED

Appendix A. Copies of the messages

* Before seeing each message, participants will view one of the four directions below according to their assigned source condition.

Condition	Expert		Peer	
	Expert 1 Government health org	Expert 2 Medical school researcher	Peer 1 Young adults	Peer 2 Influencers
Directions	Imagine that a world-renowned	Imagine that your doctor	Imagine that your best friend	Imagine that a social media

INVESTIGATOR STUDY PLAN - REQUIRED

	scientist wrote this message.	wrote this message.	wrote this message..	influencer that you follow wrote this message.
--	-------------------------------	---------------------	----------------------	--

Messages with Sidedness Manipulation

One-sided	Two-sided
Sleek design hides a deadly truth that can harm your health. Vapes contain ingredients that can cause cancer.	You may want to vape because of the sleek design. But these cool looks hide a deadly truth. Vapes contain ingredients that can cause cancer.
Vapes have ingredients that cause lung disease and cancer that are not “just vapor.”	You may want to vape because you may think it’s “just vapor.” But that’s not true. Vapes have ingredients that cause lung diseases and cancer.
Most vapes have formaldehyde, a toxic chemical. You wouldn't drink formaldehyde. Why would you vape it?	You may want to vape because you don't think it's bad for you. But don't vape. Most vapes have formaldehyde, a toxic chemical. You wouldn't drink formaldehyde. Why would you vape it?
You may have trouble breathing from vaping. Vape flavors may cause lung damage	Vapes come in cool flavors that can make you want to vape. But these flavors can cause lung damage and trouble breathing.
Chemicals in these vape flavors can hurt your lungs.	Tempting flavors like cinnamon roll and very vanilla can make you want to vape. But in truth? Chemicals in these vape flavors can hurt your lungs.
Chemicals in these vape flavors can cause cell and lung damage.	We get why you may want to vape. Vapes come in flavors like sugar and spice and everything nice. But NOPE. Chemicals in vapes can cause cell and lung damage.
People who vape are more likely to have signs of depression. What a vibe check.	You may want to vape for cool vibes. But don't trade it with your mental health. People who vape are more likely to have signs of depression. What a vibe check.
The coughing caused by lung damage from vaping? Not a good look.	You may want to vape because Influencers make vaping look cool. But don't be tricked by social media. The coughing caused by lung damage? That's not a good look.
You know what will never be cool? The lung damage caused by vaping.	You may want to vape because vaping is going viral. But you know what will never be cool? The lung damage caused by vapes.
Vape addiction is REAL. If you've been extra salty lately, that might be nicotine withdrawal.	You may want to vape for good mood. But vaping can make you feel worse. Have you or

INVESTIGATOR STUDY PLAN - REQUIRED

	your friends been extra salty lately? That might be nicotine withdrawal. Vape addiction is REAL.
Nicotine addiction means losing your independence. Don't get chained to your vape.	You may feel free when you're vaping. But nicotine addiction means losing your independence. Don't get chained to your vape.
Take a hard pass at catchy terms like "JUUL Buzz." It just means nicotine addiction.	Seeing catchy terms like "JUUL Buzz" can make you want to vape. But that just means nicotine addiction. Hard pass.
Don't get hooked by the flavors. Some pods have as much nicotine as a whole pack of cigarettes.	The flavors can make you want to vape. But don't get hooked by the flavors. Some pods have as much nicotine as a whole pack of cigarettes.
You're not just vaping flavor. Don't get hooked. Some pods contain as much nicotine as 20 cigarettes.	You may want to vape because vape companies say that you're just vaping flavor. But don't get hooked. Some pods contain as much nicotine as 20 cigarettes.
Most vape products contain nicotine. Don't get hooked by the flavors. Nicotine addiction won't give you much of a choice.	The limitless flavors can make you want to vape. But don't get hooked. Most vape products contain nicotine. Nicotine addiction won't give you much of a choice.
JUUL pods contain nicotine - as much as a pack of cigarettes. Do your friends get salty if they haven't had a hit? That's nicotine addiction.	It may be fun to hit that vape with your friends. But do your friends get salty if they haven't had a hit? That's nicotine addiction. JUUL pods contain nicotine - as much as a pack of cigarettes.
Nicotine addiction makes people moody and hard to be around, which really kills the vibe.	You may want to hit that vape with your friends. But vaping with friends leads to fighting with friends. Nicotine addiction makes people moody and hard to be around, which really kills the vibe.
Don't trade nicotine addiction to be on trend. You'll be hooked forever.	You may want to vape because it's today's big thing, but you'll be hooked forever. Don't trade nicotine addiction to be on trend.

INVESTIGATOR STUDY PLAN - REQUIRED

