Eligible participants will complete an online consent (STUDY00001220-Consent_Fact Sheet.v3.013124.docx) and tobacco use questions on a Qualtrics survey before random assignment to one of four experimental conditions in a 2 (Source: expert and peer) X 2 (Presentation: one-sided and two-sided) design. First, participants will view the source description within their assigned condition and view 18 random-ordered messages. See Appendix A. Copies of the messages. They will rate each message for perceived message effectiveness (PME),⁴⁵ a widely used measure of message acceptance by the FDA's tobacco health communication campaigns.^{46,47} They will also rate e-cigarette harm perceptions,⁴⁸ psychological reactance (resistance to the message),⁴⁹ message liking,^{50,51} and source trust.⁵² The process will repeat 18 times, once for each message. Afterwards, participants will complete posttest survey questions about their demographics, attitudes about vaping,⁴⁶ and behavioral intentions to vape.⁵³ We will check manipulation of the source manipulation by asking participants to indicate the source of the message they saw after the first three messages. After completing the study, they will receive \$4.00 via Prolific per its policies for participating in a 20-minute survey. At the end of the study, participants will be extensively debriefed about the hypothetical nature of the message source and the health harm of using any tobacco products, provided with an information sheet about the health effects of e-cigarettes and resources for the Quitlines across the U.S. See Appendix B-1 and B-2 for information about nicotine health harms and resources to quit. They will also complete a questionnaire assessing their understanding of the information regarding quitting resources. At the end of the survey, each participant is given a unique code to input into Prolific to receive compensation. We will double-check responses on our end of the survey and approve them to compensate participants.

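### Two-sided message 8, and arguably message 17, criticises the peer it is attributed to; this adds a small text-source conflict of unknown sign, mainly to peer x two-sided

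*Protocol*

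**What the plan says.** Protocol section 11 describes "random assignment to one of four experimental conditions in a 2 (Source: expert and peer) X 2 (Presentation: one-sided and two-sided) design". Appendix A splits each source into two sub-types and states that "participants will view one of the four directions below according to their assigned source condition", with the direction shown ahead of each message. The expert directions name a world-renowned scientist or the participant's own doctor ("Imagine that your doctor"). The peer directions name the best friend ("Imagine that your best friend") or a followed social media personality ("influencer that you follow wrote this message").

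The message pairs are not numbered in Appendix A; the numbers here count rows from the top.

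- Two-sided message 8 gives as its reason for vaping: "You may want to vape because Influencers make vaping look cool". It then tells the reader not to be taken in by social media.
- Two-sided message 17 offers vaping with friends as the reason and continues: "But vaping with friends leads to fighting with friends".
- Two-sided message 16 opens "It may be fun to hit that vape with your friends" and then asks whether friends become irritable without a hit.
- Two-sided message 10 asks in passing about the reader or the reader's friends.

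Protocol section 13 averages each measure over all messages and ranks message types on those averages, with measures equally weighted. The SAP repeats the averaging. Neither document mentions the overlap between message text and assigned author, or plans an analysis without these messages.

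**The concern.** A 2 x 2 factorial reads the source x sidedness combination cleanly only if the two factors are the only things that change between cells. Here a third property changes with them: whether the text criticises its own supposed author. It is present in some peer x two-sided material and in no expert cell. Randomising participants or message order cannot remove it, because it is built into the stimuli.

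Perceived message effectiveness (the measure of message acceptance, a primary outcome), reactance, liking and source trust are all rated message by message. Source trust is the most exposed when an author appears to accuse himself. Harm perceptions, the other primary outcome, are about e-cigarettes and not about the author, so they are less directly exposed.

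What is at stake is the ranking of the four message types. The stated rule ranks averages with no threshold for a meaningful difference, so a small built-in shift can decide between two close cells, and recruiting more participants would not shrink it.

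**Working it through.** **The plan's own figure.** Four source directions x 2 presentation types = 8 conditions; 8 x 50 = 400 per vaping status; 400 x 2 = 800. This agrees with the SAP. Each cell of the 2 x 2 therefore holds 2 x 50 = 100 participants per vaping status. The rank-stability simulation behind n = 50 cannot be reproduced, because its input distributions are not given.

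**Comparing the pairs with the source directions**

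| Row | Two-sided text | One-sided partner | Affected arm | Strength |
|---|---|---|---|---|
| 8 | Influencers given as the reason; social media called a trick | No mention of either | Peer 2 | Clear |
| 17 | Friends as the reason, then as a cause of fights | No mention of friends | Peer 1 | Arguable |
| 16 | Friends as the appeal, then criticised | Same criticism of friends | Peer 1 | Weak: largely cancels |
| 10 | Friends mentioned in passing | No mention of friends | Peer 1 | Weak |

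Row 9 speaks of vaping going viral but names no source, so it is not counted. No row in either version names a scientist or doctor.

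**Dilution in the 18-message mean.** Let d be the shift in one rating caused by a conflict. The documents do not give d. Half of the peer participants are in each sub-type, so:

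- Row 8 alone: (1/18)/2 = 1/36 = 0.028 x d.
- Rows 8 and 17: (1/18 + 1/18)/2 = 2/36 = 0.056 x d.
- Rows 8, 10 and 17: (1/18 + 2/18)/2 = 3/36 = 0.083 x d.
- Adding row 16 in both versions: 4/36 - 1/36 = 3/36, again 0.083 x d, if row 16 shifts both versions equally.

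The expert cells contribute zero, so each figure is also the spurious source x sidedness difference.

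**In points.** Assume a 5-point rating and d = 0.5 to 1.5; neither is in the documents for these outcomes. Rows 8 and 17 give 0.056 x 0.5 = 0.03 to 0.056 x 1.5 = 0.08. Row 8 alone gives 0.014 to 0.042. With row 10 added the range is 0.083 x 0.5 = 0.04 to 0.083 x 1.5 = 0.13.

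**Against sampling error.** Work in SDs of a single rating, with an assumed between-message correlation r of 0.3 to 0.7. The SD of a participant's 18-message mean is sqrt(r + (1 - r)/18) = 0.58 to 0.85. The standard error of a difference between two cells of 100 is that value x sqrt(2/100) = 0.082 to 0.120. For the four-cell interaction it is that value x sqrt(4/100) = 0.116 to 0.169.

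For assumed d = 0.25 to 1.0 SD, rows 8 and 17 shift the pooled peer x two-sided mean by 0.014 to 0.056 SD, below both standard errors throughout. Only the broadest count exceeds one: all four rows at d = 1.0 SD shift the peer x two-sided mean by 4/36 = 0.111 SD, which passes the two-cell standard error at r = 0.3 (0.082) but not at r = 0.7 (0.120). The matching interaction, 0.083, stays below 0.116.

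**The case against.** The strongest reply is that only message 8 plainly criticises its assigned author. A best friend can naturally write about the reader's friends, and nothing in the text says the author is the friend who vapes. Message 10 blames nobody. Message 16 criticises friends in both versions, so most of any effect cancels between one-sided and two-sided. This stands, and it is why the size is taken from messages 8 and 17 only, with 17 treated as arguable.

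A second reply is that other mismatches exist. Two-sided message 6, with its slangy sympathy for wanting to vape, reads oddly from a scientist or doctor, and its one-sided partner lacks that tone. That is fair, but it is a mismatch of register; the text does not accuse its own author.

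A third is that a real influencer might well write message 8. Even so, self-criticism would then be an extra ingredient found in one cell and credited to source or sidedness.

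A reader might infer that the peer x two-sided cell is handicapped, and that this is the very cell the hypothesis predicts to be best for vapers. The documents support neither step. Self-implicating text may lower ratings or may read as candour. The vaper hypothesis in Protocol section 4 is garbled as printed and names no clear comparator; its peer and two-sided direction has to be inferred from the Background. Nor is mention of friends confined to two-sided text, since one-sided message 16 has it too.

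**Conclusion.** The point holds in a limited form. Message 8 clearly, and message 17 arguably, adds a text-source conflict to peer x two-sided that has no counterpart in the one-sided partners or the expert cells. The planned averaging cannot separate it from source or sidedness. The spurious interaction is 0.056 x d on those two messages, or 0.083 x d if message 10 is added. In points this is 0.03 to 0.08, or 0.04 to 0.13 with message 10. The sign is unknown, and the size rests wholly on the assumed d and the assumed 5-point scale.

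It is probably under one standard error, and it is diluted further when ranks are averaged with the psychophysiological measures of Part 2. It is unlikely to create or hide a clear difference. It could reorder message types whose means are close. This is a cheap improvement to make, not a flaw that undermines the study.

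**What to change.** Before launch, reword two-sided message 8 so that its reason for vaping names neither influencers nor social media, and preferably reword two-sided message 17 so that it does not turn on friends. Each should still acknowledge a reason for vaping, since that is what makes it two-sided. Stripping social reasons from all four messages is not advised: the Background's own illustration of a two-sided message is that others are using the product.

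If the texts are already fixed, keep the 18-pair analysis as planned. Prespecify a sensitivity ranking that drops pairs 8 and 17 from every arm (16 pairs), and a broader one that also drops 10 and 16 (14 pairs). Report whether any message-type rank changes.

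The cost of rewording is a slight departure from the previously tested message text. The sensitivity analysis needs no new data, but it uses fewer messages per participant than the 18 assumed in the SAP's rank-stability simulation, so its ranks will be somewhat less stable.
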